## 4.2 OTHER TREATMENTS, EMERGENCY PROCEDURES, RESTRICTIONS

### 4.2.1 Other treatments and emergency procedures

Throughout the duration of the trial, patients should continue to take insulin alone or in combination with acceptable OADs as background therapy.

Acceptable basal insulins should have duration of action up to 24 h such as insulin degludec, insulin glargin, insulin detemir or NPH (neutral protamine hagedorn) insulin. The background medication of OADs should remain unchanged throughout the study. Acceptable pre-mixed insulins could be once or twice daily posology only. The total prescribed insulin dose should not be changed by more than 10% of the baseline value in the 24 weeks after randomisation unless rescue therapy criteria for treatment of hyperglycemia are met or in case of hypoglycemia requiring insulin dose reduction beyond the defined limits. The background medication will not be provided as part of the clinical trial supplies.

The patients can take their background medication as they are used to and should have the same habits of dosing throughout the trial, where it is suggested that basal insulin is always given in the evening. Morning dose of OADs/any permitted pre-mixed insulin and study medication should be taken after the visits blood sample taken.

#### Hyperglycemia

If the following FPG criteria in [Table 4.2.1: 1](#) are met and confirmed, investigators may increase the insulin dose for the treatment of hyperglycemia according to their discretion and the change should be documented in the eCRF [[R08-2669](#)].

The first choice of rescue therapy should be the adjustment of insulin therapy. Its dosage will be left to the discretion of the investigator. However the insulin regimen and daily number of injections should remain unchanged. In very rare cases, adjustment of background therapy or addition of another oral anti-diabetic medication except SGLT-2 inhibitors would be appropriate. Such cases should be discussed with the Manager (CTM) or the Clinical Trial Leader (CTL).

Table 4.2.1: 1 FPG criteria for hyperglycemia

Week	Visit	FPG level
Week 1- 4	up to Visit 4 (included)	>270 mg/dl (>15.0 mmol/l) after overnight fast
Week 4-12	up to Visit 6 (included)	>240 mg/dl (>13.3 mmol/l) after overnight fast
Week 12-24	after Visit 6 until Visit 8	>200 mg/dl (>11.1 mmol/l) after overnight fast

To confirm the above results, there should be a minimum of two measurements, at least one of which performed after an overnight fast at the investigational site, and on a different day to the initial measurement.

A FPG, HbA1c sample should be taken before initiation of rescue therapy and sent to central lab for analysis. The HbA1c sample is not required if a sample has been taken and sent to the central lab for analysis within the last 4 weeks.

If, in the Investigator's clinical opinion, no further effect from the rescue medication is anticipated, and the patient's hyperglycemia cannot be controlled, the patient should be discontinued from the treatment as specified in [section 3.3.4](#).

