## FLOW CHART

Trial Periods	Screening	Run-in	Randomised Treatment					Follow-up
Visit	1	2	3	4 N	5 N	6 N	7 N	8 (EoT A )
Weeks	-3	-2	0	4	8	12	18	24
Study Day	-21	-14	1	29	57	85	127	169
Time window for visits	±7 days	-7 days	0	±7 days	±7 days	±7 days	±7 days	+ 7 days
Informed consent	X							
Demographics B	X	X						
Medical history	X							
In-/Exclusion criteria	X	X	X					
Physical examination		X						X
Vital signs	X	X	X	X	X	X	X	X M
Height	X							
HbA 1c	X		X	X	X	X	X	
Home Blood Glucose Monitoring C		X	X	X	X	X	X	X
Dispense placebo run-in kit D		X						
Randomisation (via IRT)			X					
Weight	X		X	X	X	X	X	
Waist circumference			X					X
Diet and exercise counselling E		X	X	X	X	X	X	
12 lead-ECG F			X					X
8-point glucose profile L			X			X		X
Pregnancy test G	X		X		X			X
Glomerular filtration rate H	X		X		X			X
Fasting C-peptide	X							
Safety lab tests I (urine and blood)	X I	X	X			X		X M
FPG		X	X	X	X	X	X	X M
2-hour PPG test J			X					X
Lipid lab panel			X					X
MTT test (including Insulin + c-peptide) J			X					X
Dispense trial drugs D			X	X	X	X	X	
All AEs/SAEs/AESIs K	X	X	X	X	X	X	X	X
Concomitant therapy	X	X	X	X	X	X	X	X
Compliance check			X	X	X	X	X	
Completion of patient participation								X

- A Patients who discontinue trial treatment prematurely should undergo the End of Treatment (EOT) visit as soon as possible and allow to attend all clinic visits up to the FUP Visit thereafter in order to collect all the data as other treatment completed patients.
- B Only screening relevant demographics (gender, date of birth, race and ethnicity) at Visit 1. Smoking and alcohol status could be collected at Visit 2.
- C Instruction and training of the patient to use the device at Visit 2. A full overnight fast (nothing to eat or drink except water for at least 10 hours) for all planned tests. Daily measurements during Run-in and Follow-up. During the treatment period a weekly test is recommended. During the whole trial participation, additional measurements should be done in case of hypo- or hyperglycemia related symptoms without fasting state required.
- D At all visits, the respective kit number has to be allocated to the patient via IRT.

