## **5. ASSESSMENTS**

### **5.1 ASSESSMENT OF EFFICACY**

#### HbA1c

Blood samples for the determination of HbA1c at the central laboratory will be taken at all the visits except Visit 2, the blood sample can be taken at any time during the visit. For the determination of HbA1c, 3 mL of blood will be collected. The samples will be analysed at a central laboratory having a National Glycohaemoglobin Standardization Program (NGSP) Level I certificate. Further details about sample handling, shipment, and assay procedures can be found in the ISF (Lab manual).

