6.6.2 Methods of data selection

Original result (OR) analysis

Original result analysis implies the analysis of data exactly as observed. OR analysis will be performed on endpoints that are either not affected by patients' antidiabetic rescue medication use or if it is not meaningful to apply any imputation rule on them for replacing the missing values.

Observed cases (OC) analysis

For all efficacy endpoints, it is planned to analyse only the available data that were observed while patients were on treatment, i.e., excluding the missing data. In other words, OC analysis will be performed and missing data in this analysis will not be replaced.

For all efficacy endpoints, this OC-technique will set all values measured after antidiabetic rescue medication taken to missing (antidiabetic rescue medication as defined in [section 6.6.1](#)).

Observed cases analysis including data after treatment discontinuation and rescue therapy (OC-AD)

To mimic an intent-to-treat (ITT) analysis, post-treatment as well as post-rescue measurements may also be included. This will be done as a secondary analysis of the primary endpoint with OC as the imputation rule.

Non-completers considered failure (NCF)

For binary endpoints, like a treat to target response of $\text{HbA1c} < 7.0\%$, a conservative method to replace missing values is to consider them as "failures". Missing data due to early discontinuation per the completer definition will be replaced as "failure" (i.e. $\text{HbA1c} \geq 7.0\%$) up to the planned final visit to be reached by all patients. Values obtained after rescue medication was started are also replaced as "failure".

A multiple imputation (MI) approach will also be used as a sensitivity analysis for the primary endpoint. Further details can be found in [Section 7.4.2](#).

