6.7 BASELINE, TIME WINDOWS, AND CALCULATED VISITS

With regard to efficacy and safety endpoints, the term “baseline” refers to the last observed measurement prior to administration of any randomised study medication.

Measurements taken prior to the first intake of randomised study medication will be considered pre-treatment values. Pre-treatment values will be assigned to a visit according to the nominal visit number as recorded on the eCRF or as provided by the laboratory.

In general, the date and clock time of the first drug administration will be used to separate pre-treatment from on-treatment values; Measurements taken after the first intake of randomised study medication will be considered on-treatment values if they have been obtained up to end of the parameter specific follow-up period as defined in [Table 6.7:1](#) below and will be assigned to the randomised study medication for efficacy analyses and to the first study medication taken for safety analyses.

Proprietary confidential information © 2021 Boehringer Ingelheim International GmbH or one or more of its affiliated companies

Table 6.7:1 Endpoint specific follow-up period for the assignment to treatment phase

Endpoint	Last day of assignment to treatment phase (days after study medication stop date)
Efficacy	
HbA _{1c}	7
FPG	1
Body weight	1
Blood pressure (systolic, diastolic)	1
PPG	1
MDG	1
C-peptide	1
Biomarkers of insulin resistance and secretion	1
Waist circumference	7
Safety	
Adverse events	7
Safety laboratory measurements	3
Pulse rate	1

Measurements taken after the end of the endpoint specific follow-up period and after the last intake of study medication will be considered post-treatment values.

On-treatment efficacy and safety measurements will be assigned to visits based on time windows around the planned visit dates. These time windows are defined based on the planned number of days after the date of first administration of study medication (see [Table 6.7:2](#)).

Proprietary confidential information © 2021 Boehringer Ingelheim International GmbH or one or more of its affiliated companies

Table 6.7:2 Time windows for on-treatment efficacy measurement scheduled for each on treatment visit

Visit number	Visit label	Planned days	Time window (actual days on treatment)	
			Start	End ^A
3	Baseline	0	NA	1 ^B
4	Week 4	28	2	42
5	Week 8	56	43	70
6	Week 12	84	71	105
7	Week 18	126	106	147
8	Week 24/EOT	168	148	Study medication stop date + X days

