^A In case of premature discontinuation of the study medication an early EoT visit has to be performed. If such an EoT Visit falls into the time window of a previous visit, measurements will be assigned to this previous visit and the visit value will be determined as described below. In this case the time window for the visit that includes the early EoT visit will end X days after the study medication stop date, including Day X. The definition of X is endpoint specific, cf. [Table 6.7:1](#). Patients will then be asked to continue in the study according to the visit schedule. Off-treatment measurements will be assigned to visits in the same manner. No time window for optional visit is planned.

^B Only values taken prior to the start of treatment with randomised study medication can be considered baseline values. Time windows will be used for assignment of measurements to scheduled visits.

Reasons to base the time windows on the actual treatment start date rather than the randomisation date are:

- If first intake of study medication shows a large delay by e.g. more than one week after the date of randomisation, a measurement taken four weeks after randomisation rather reflects the drug effect after three weeks than after four weeks and thus may underestimate the treatment effect at this visit.
- With large delays of the introduction of study medication after the randomisation, the time window for the first on-treatment visit could include times the patient was not yet on study medication.

The time window for the first visit after randomisation starts on the day after the first intake of study medication. This maximises the number of measurements used in by visit analyses may lead to an underestimation of the treatment effect at the first visit for parameters that react slowly on treatment.

The midpoint between two on-treatment visits defines the end of a time window, with the midpoint being included in the time window of the preceding visit. The end of the time window of the last on-treatment visit (end of treatment (EoT)) is endpoint dependent ([Table 6.7:1](#)).

Repeated and unscheduled efficacy and safety measurements will be assigned to the nominal visits and listed in the SDL according to the time windows described above. Only one observation per time window will be selected for analysis at an on-treatment visit - the value

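### The 4-week waiver of the pre-rescue HbA1c sample is not aligned with the SAP visit windows, so some rescued patients can lack an on-treatment value that was obtainable

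*Protocol*

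**What the plan says.** Protocol 4.2.1 (Hyperglycemia) deals with the moment before rescue. An FPG and HbA1c "sample should be taken before initiation of rescue therapy and sent to central lab for analysis". The next sentence relaxes this for HbA1c only: the "sample is not required if a sample has been taken and sent to the central lab for analysis within the last 4 weeks". FPG has no such exception.

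Scheduled HbA1c samples "will be taken at all the visits except Visit 2" (protocol 5.1), so the Visit 3 baseline sample also counts as a recent sample.

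In the primary analysis (protocol 7.2.2.1), HbA1c measured after rescue starts is set to missing. SAP 6.6.2 repeats this for the observed-cases approach: "this OC-technique will set all values measured after antidiabetic rescue medication taken to missing".

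SAP 6.7 then says: "On-treatment efficacy and safety measurements will be assigned to visits based on time windows around the planned visit dates". Unscheduled measurements are assigned in the same way. One value per window is kept, namely the one nearest the planned day.

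**The concern.** A pre-rescue HbA1c is the last value from that patient that the primary analysis can use. Whether it fills a visit depends on the SAP window in which the rescue falls. Whether it has to be drawn depends on the days since the previous sample. These two rules do not match: each window opens less than 28 days after the preceding visit, so for a time the waiver still applies although the patient is already in a new, empty window.

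At stake is an observed on-treatment value in patients who are failing on treatment. Their missingness is tied to the outcome, and the missing-at-random assumption leans on their latest observed value. The multiple-imputation sensitivity analysis (protocol 7.2.2.2) also uses the last on-treatment value as a predictor, so it would work from an older value or from none.

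**Working it through.** **The plan's own figures.** A two-sample t-test with difference 0.62, SD 1.1 and two-sided alpha 0.05 needs 68 per arm for 90% power (I obtain 90.4%; Table 7.5: 1 prints 90.3). Then 68 / (1 - 0.08 x (1 - 0.4)) = 71.4, rounded up to 72. The sample size reproduces.

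**Inputs for the overlay**
- Waiver length: 28 days after the last central-laboratory HbA1c (protocol 4.2.1).
- Visit days from the Flow Chart: "Study Day -21 -14 1 29 57 85 127 169". Visits 3 to 8 are therefore on days 1, 29, 57, 85, 127 and 169, with plus or minus 7 days for Visits 4 to 7.
- SAP windows (Table 6.7:2): Week 4 is days 2-42, Week 8 is 43-70, Week 12 is 71-105, Week 18 is 106-147. The last row reads "Week 24/EOT 168 148 Study medication stop date + X days". The boundaries follow from the rule "The midpoint between two on-treatment visits defines the end of a time window", for example (126 + 168)/2 = 147.

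**Rule.** A rescue day is exposed if it lies in the next visit's window, is at most 28 days after the previous sample, and comes before the next scheduled sample.

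| Previous sample | Waiver runs to | Next window opens | Exposed days | Count |
|---|---|---|---|---|
| Visit 3, day 1 | 29 | 2 (Week 4) | 2-28 | 27 |
| Visit 4, day 29 | 57 | 43 (Week 8) | 43-56 | 14 |
| Visit 5, day 57 | 85 | 71 (Week 12) | 71-84 | 14 |
| Visit 6, day 85 | 113 | 106 (Week 18) | 106-113 | 8 |
| Visit 7, day 127 | 155 | 148 (Week 24) | 148-155 | 8 |

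Total: 27 + 14 + 14 + 8 + 8 = 71, and 71/168 = 42%.

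**Sensitivity to timing.** The SAP counts planned days as 28, 56, 84, 126 and 168, one lower than the Flow Chart. On that count the on-time total is 66 days (39%), and the Week 24 range is 148-154. Over both counts and visit shifts of -7 to +7 days, the total runs from 31 to 100 days (18% to 60%). The Week 24 range shrinks to day 148 alone (none on the SAP count) if Visit 7 is 7 days early, and extends to day 162 if it is 7 days late.

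**Where nothing is lost.** After an on-time Visit 7, a waived sample on days 128-147 costs nothing, because the Visit 7 value already fills the Week 18 window. After day 155 the waiver has lapsed and the sample is required.

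**Number of values.** The plan gives no split of the 8% between rescue and discontinuation. Assume that all 8% are rescues, spread evenly over 168 days:
- Censored patients per arm: 72 x 0.08 = 5.76.
- All windows: 5.76 x 71/168 = 2.4 values per arm.
- Week 4 window only: 5.76 x 27/168 = 0.93.
- Week 24 window only: 5.76 x 8/168 = 0.27 (0.03 to 0.51 for 1 to 15 exposed days).

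**Power.** Effective n from 72 is 72 x (1 - 0.08 x 0.6) = 68.54, power 90.6%.
- Week 24: raising the information content of 0.27 patients from 0.4 to 1 adds 0.16 and gives about 90.7%. At 15% censoring, power rises from 89.3% to at most 89.6%.
- Early rescues: if 0.93 patients carried 0 instead of 0.4, effective n would fall by 0.37 to 68.17, power 90.4%. At 15% censoring the corresponding fall is from 89.3% to 89.0%. Both overstate the loss, since a sample on days 2-28 would hardly carry 0.4 of a completer's information about Week 24.

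At the planned 8%, the two effects together stay under 0.3 points.

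**The case against.** The strongest case against is that this is an optional extra sample with almost no effect. Much of that stands.

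- A reader might infer that the waiver discards data. It does not. It removes a requirement; a site may still draw the sample, and no collected value is deleted.
- A reader might also infer that every rescue from day 148 onward loses its Week 24 value. The exposure ends when the waiver lapses, at day 155 with Visit 7 on time.
- Even spread is doubtful. FPG and HbA1c are both taken at every treatment visit, so a rescue prompted by a visit FPG and confirmed quickly has an HbA1c in the same window. Exposed days start 14 to 21 days after Visits 4 to 7. Weekly home testing leaves some risk. For days 2-28, the FPG criterion is at its highest (above 15.0 mmol/l) and the run-in excludes fasting glucose above 13.9 mmol/l, so early rescue may be rarer than assumed.
- The 8% includes discontinuations. SAP 6.6.1 also counts insulin decreases and other dose changes as rescue, to which the hyperglycaemia sampling rule does not apply.
- The model still has an HbA1c at most 4 weeks old. That it would usually be lower than the missed value is plausible, but no figure in the documents shows it.
- Post-rescue values enter the effectiveness analysis, and rescued patients count as non-responders for HbA1c below 7.0%.
- Recovery is not assured. The SAP does not state whether censoring precedes selection of one value per window. If selection came first, a Visit 8 value could displace the pre-rescue one and then be censored. SAP 6.6.1 suggests exclusion first but does not say so.

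These points limit the size. They do not align the two rules, and for days 2-28 the only recent sample may be the baseline itself.

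**Conclusion.** The misalignment is real and follows from the documents alone. With on-time visits it covers about 71 of 168 treatment days (42%; 18% to 60% over visit shifts and day counts). The most consequential part is days 2-28, where a patient may have no pre-rescue post-baseline HbA1c and so contribute nothing to the primary MMRM.

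The size is small: about 2.4 visit values per arm and about 0.27 Week 24 values per arm. This rests on two assumptions that the documents do not supply: every censored patient is a rescue, which is a ceiling, and rescues are evenly spread, which could err either way.

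Two stronger readings are not supported. The trial is not underpowered because of this, since less than 0.3 points is at stake at the planned censoring rate. Nor is it established that an early-rescued patient leaves the mITT set: the SAP requires at least one on-treatment HbA1c, but its on-treatment periods are defined by drug intake, so a post-rescue value could satisfy that condition while remaining censored in the model.

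This is a low-cost improvement that reduces outcome-related missing data. It does not correct an error in the primary analysis.

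**What to change.** 1. In protocol 4.2.1, delete the 4-week exception, so that HbA1c is drawn with the FPG sample already required before rescue. Alternatively, limit the exception to cases where a post-baseline HbA1c already lies in the same SAP visit window. The words post-baseline are needed so that the Visit 3 sample no longer triggers it. Outright deletion is easier for sites, which do not work with SAP windows.
2. In SAP 6.7, add one sentence: post-rescue values are set to missing before the one value per window is selected. Without it, the extra sample might not reach the analysis.

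The cost is one additional 3 mL tube at a blood draw that takes place anyway, for the few rescued patients, plus one edited sentence in each document. Rescue criteria, timing and treatment are unchanged.

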### **Hypoglycemia**

If the patient is experiencing hypoglycemia (criteria see [section 5.2.7](#)), the investigator should review the HBGM log to determine the appropriate approach to reduce occurrences of hypoglycemia (e.g., encouraging the patient not to skip meals, increasing carbohydrate intake if increasing exercise, decreasing or adjusting the patient's permitted antidiabetic therapy).

In the case of hypoglycemia that may put patient on risk (e.g. repeated symptomatic hypoglycemia or severe hypoglycemia), appropriate adjustment of anti-diabetic therapy such as a dose reduction / discontinuation of ongoing rescue medication or existing background therapy should be initiated. Reduction or discontinuation of ongoing rescue medication should be considered before a reduction in the dose of existing background therapy.

Reduction of insulin dose should be the first choice among the existing background therapy while the insulin regimen and daily number of injections should remain unchanged.

Any rescue medication will be recorded in the source documents and on the appropriate pages of the eCRF.

Rescue medication will not be provided as part of the clinical trial supplies.

Any additional treatment, that does not qualify as a rescue medication, and is considered necessary for the patient's welfare may be given at the discretion of the Investigator.

Exceptions to this are the restrictions described in [section 4.2.2](#).

In this trial, the background therapy (i.e. insulin alone or in the combination with OADs) are considered as non Auxiliary Medicinal Product (AMP).

There are no special emergency procedures to be followed.

#### **4.2.2      Restrictions**

##### **4.2.2.1    Restrictions regarding concomitant treatment**

The following restrictions are applicable during the screening, run-in and treatment period:

- Treatment with anti-obesity drugs, herbal medications with antidiabetic effects or systemic steroids due to their influence on glucose metabolism. However, one off or short-term use (i.e.  $\leq$  1 week's duration) of systemic steroids will be permitted as well as therapy with non-systemic steroids such as inhaled or local steroids.
- For patients taking thyroid hormones, any change in the dose should be avoided. If dose changes do occur, then they should be recorded in the source documents and in the eCRF.
- SGLT-2 inhibitors are not allowed even as a rescue therapy.

Please also refer to [section 3.3.3](#) regarding the permitted use of antidiabetic agents pre-trial.

